3.3 Subject Early Termination

Subject early termination reasons will be summarized.

3.4 Protocol Deviation

Protocol deviations will be summarized for subjects in whom a protocol deviation was reported.

Statistical Analysis Plan

3.5 Descriptive Endpoints or Additional Data

3.5.1 Descriptive endpoints

The following descriptive endpoints will be reported:

Safety

- Proportion of subjects with device, procedure or stimulation-related serious adverse events and non-serious adverse events among subjects who receive the permanent implant
- Proportion of subjects who have adverse events related to the trial implant procedure among subjects who fail the trial neurostimulator phase
- Summary of procedure-related serious adverse events and non-serious adverse events by implanter experience

Effectiveness

- Percent change from baseline to 1, 3, and 6 months post-permanent implant for overall pain intensity measured using the Visual Analog Scale (VAS)
- Change from baseline to 1, 3, and 6 months post-permanent implant for physical function measured using the PROMIS-29 Profile
- Change from baseline to 1, 3, and 6 months post-permanent implant for quality of life measured using the PROMIS Global Health Scale
- Change from baseline to 1, 3, 6 and 12 months post-permanent implant for neuropathic pain measured using the Neuropathic Pain Scale (NPS)
- Change from baseline to 1, 3, 6 and 12 months post-permanent implant for sleep disturbance, anxiety, depression, fatigue, ability to participate in social roles and activities, pain interference and pain intensity measured using the PROMIS-29 Profile
- Patient Global Impression of Change (PGIC) at 1, 3, 6 and 12 months post-permanent implant

The analysis population for these descriptive endpoints will include primary analysis population subjects with available data and no imputation will be implemented.

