**Clinical Investigational Plan**

at up to 45 centers in the United States. A maximum of 426 subjects will be enrolled to achieve 319 subjects with a permanently implanted system, which will account for expected attrition, to yield 287 subjects for the primary analysis at 12 months post-implant (See Section 10.9 Sample Size for full details). After the last subject with a permanently implanted device reaches the 12-month study visit or crosses the 12-month study visit window, the endpoint analysis will be conducted and reported to the FDA.

After the subject signs the informed consent, s/he will be screened according to the inclusion/exclusion criteria and will undergo a baseline evaluation. Those subjects who meet the criteria for participation will undergo a trial of the DRG Neurostimulation System to assess response to DRG stimulation. Only subjects who report a 50% or greater reduction in overall pain intensity through direct patient-reported percentage of pain relief will receive the permanent implant. Device activation will occur according to the site's standard of care and may occur at the time of permanent system implant. Subjects will then return to the office for follow-up at 1, 3, 6 and 12 months post-permanent implant. Figure 2 below outlines subject flow through the study.

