## Clinical Investigational Plan

- Change from baseline to 1, 3, 6 and 12 months post-permanent implant for sleep disturbance, anxiety, depression, fatigue, ability to participate in social roles and activities, pain interference and pain intensity measured using the PROMIS-29 Profile
- Patient Global Impression of Change (PGIC) at 1, 3, 6 and 12 months post-permanent implant

The analysis population for these descriptive endpoints will include subjects with available data.

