1.3 Clinical Investigation Design

This study is a prospective, multicenter, single arm, observational, post-approval study with follow-ups at 1, 3, 6 and 12 months post-permanent implant. [REDACTED]

[REDACTED]

[REDACTED]

After the subject signs the informed consent, s/he will be screened according to the inclusion/exclusion criteria and will undergo a baseline evaluation. Those subjects who meet the criteria for participation will undergo a trial of the DRG Neurostimulation System to assess response to DRG stimulation. For purposes of accounting, subjects are considered enrolled in the study only after they receive the trial system implant. Subjects who fail the trial procedure are considered as screen failures. Only subjects who report a 50% or greater reduction in overall pain intensity through direct patient-reported percentage of pain relief at the of trial evaluation period will receive the permanent implant. Device activation will occur according to the site's standard of care and may occur at the time of permanent system implant. Subjects will then return to the office for follow-up at 1, 3, 6 and 12 months post-permanent implant.

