2.3 Endpoint Analysis

2.3.1 Primary Endpoint

The hypothesis is stated as follows:

[REDACTED]

where p is the 12-month serious adverse event rate for subjects who receive the permanent Axium or Proclaim DRG IPG. The hypothesis will be tested at the 5% significance level.

The primary endpoint analysis will be conducted using Kaplan-Meier method on subjects who received the permanent Axium or Proclaim DRG IPG (primary analysis population). The serious adverse events include adverse events which occur after permanent implant and CEC adjudicates as serious events.

The primary endpoint includes all serious adverse events, including ones related to the neurostimulation device or procedure as well as any unrelated serious adverse events.

[REDACTED]

Statistical Analysis Plan

[REDACTED]

[REDACTED]

[REDACTED]

The 12-month (365 days) serious adverse event rate will be estimated using Kaplan-Meier method with a 95% upper confidence bound (UCB) estimated using log-log transformation. If the 95% UCB is less than the [REDACTED], the null hypothesis will be rejected.

[REDACTED]

[REDACTED]

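### SAP 3.5.1 assigns all descriptive endpoints to permanent-IPG recipients, so the adverse-event endpoint for subjects who fail the system trial has, read literally, no denominator

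*SAP*

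**What the plan says.** SAP 3.5.1 lists three safety and six effectiveness endpoints. The second safety endpoint is: "Proportion of subjects who have adverse events related to the trial implant procedure among subjects who fail the trial neurostimulator phase". After the full list comes one population sentence with no exception for any item: "The analysis population for these descriptive endpoints will include primary analysis population subjects with available data and no imputation will be implemented".

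SAP 2.3.1 says whom that population contains: "subjects who received the permanent Axium or Proclaim DRG IPG (primary analysis population"). Protocol 10.1 uses the same definition.

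SAP 1.3 sets the condition for a permanent implant, which goes to "Only subjects who report a 50% or greater reduction in overall pain intensity through direct patient-reported percentage of pain relief" in the system trial. It adds: "Subjects who fail the trial procedure are considered as screen failures". It also counts a subject as enrolled once the trial system has been implanted.

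Protocol 10.3 carries the same descriptive list with a wider rule: "The analysis population for these descriptive endpoints will include subjects with available data".

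**The concern.** The endpoint on trial failures concerns people who cannot belong to the population the SAP assigns to it. A programmer who followed SAP 3.5.1 to the letter would have nobody in the table. One who followed the endpoint's own wording would depart from the stated population rule. Either way the choice would be made at analysis, not in the plan.

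This is the only named endpoint devoted to subjects who were exposed to the trial-lead procedure and went no further. The study is a condition of approval and its primary objective is safety, so the final report should be able to give that proportion. Protocol 10.7 already asks for it in the annual progress reports. A final report that kept literally to SAP 3.5.1 could not repeat a figure given each year.

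The third safety endpoint, procedure-related events by implanter experience, falls under the same sentence. Read literally it too is limited to implanted subjects, which is narrower than Protocol 10.3.

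**Working it through.** This is mainly a question of set membership.

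**Inputs**
- A = the population assigned to every descriptive endpoint = primary analysis population with available data (SAP 3.5.1).
- Primary analysis population = received a permanent IPG (SAP 2.3.1, Protocol 10.1).
- B = the denominator named in the endpoint = subjects who fail the system trial (SAP 3.5.1).
- Permanent implant is given only after a successful system trial (SAP 1.3, Protocol 8.7).
- Planned flow (Protocol 5.0): "A maximum of 426 subjects will be enrolled to achieve 319 subjects with a permanently implanted system", and "to yield 287 subjects for the primary analysis at 12 months post-implant".

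**Step 1: the plan's own flow.** The attrition rates are not visible, so I solved for them. This is a consistency check, not an independent reproduction.
- Implant to 12 months: 1 - 287/319 = 10.0%. Forward: 287/(1 - 0.10) = 318.9, rounded up to 319.
- Trial to implant: 1 - 319/426 = 25.1%. Forward, with 25%: 319/(1 - 0.25) = 425.3, rounded up to 426.

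The flow is coherent, and nothing here disputes it.

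**Step 2: denominator as written.** Members of A have a permanent IPG. Members of B, under SAP 1.3, do not. A ∩ B is empty, so the denominator is 0. Protocol 10.1 also gives a narrower analysis population (an SAE after implant, or completion of the 12-month visit). It too requires a permanent implant, so the result is the same. Only a trial failure implanted in deviation from the plan could enter the set, and that is not a planned denominator.

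**Step 3: denominator under Protocol 10.3.** Subjects with available data include trial failures. At the planned flow, 426 - 319 = 107 subjects are not implanted, and 107/426 = 25.1%. This is an upper planning value: it takes the maximum of 426 as reached and every non-implanted subject as a trial failure, although some may not proceed for other reasons.

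**Step 4: what that denominator could show.** Exact 95% Clopper-Pearson limits at n = 107:

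| Subjects with event | Proportion | 95% limits |
|---|---|---|
| 0 | 0% | upper limit 3.4% |
| 5 | 4.7% | 1.5% to 10.6% |

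For 0 events the upper limit is 1 - 0.025^(1/107) = 0.034. The event counts are illustrations; the documents give no expected rate.

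**The case against.** The strongest reply is that the endpoint carries its own denominator. A specific denominator would ordinarily prevail over a general closing sentence, and that sentence follows the effectiveness list, where its remark on imputation fits best. An empty table is the least likely outcome in practice. SAP 2.1.1 is also redacted, and SAP 2.2.2 refers to table mock-ups that are not visible and may state the right denominators. This stands as evidence of intent. It does not remove the conflict, because the visible sentence covers all the listed endpoints, the visible definition in SAP 2.3.1 agrees with Protocol 10.1, and no visible text makes an exception.

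Four stronger readings are tempting, and the documents do not support them.

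- *A study objective would return no result.* No stated objective concerns trial failures. The primary objective covers permanent-IPG recipients; the secondary ones cover pain, function and quality of life. This is a descriptive endpoint with no test attached.
- *The events of trial failures would go unreported.* SAP 3.2 summarizes adverse device effects, serious and non-serious, for all enrolled subjects, and SAP 5.0 defines these to include procedure-related events. Protocol 10.7 lists both affected safety endpoints for the annual reports without restricting them to implanted subjects. SAP 3.2 does not, however, give the proportion among trial failures.
- *Calling trial failures screen failures removes them from the enrolled summaries in SAP 3.1 and 3.2.* SAP 1.3 counts trial-system recipients as enrolled in the sentence just before that label, and nothing says that screen failures leave those summaries.
- *The implanter-experience summary wrongly loses a quarter of trial procedures.* Neither document says that this summary must pool trial and permanent procedures. What can be said is that SAP 3.5.1 is narrower here than Protocol 10.3.

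**Conclusion.** The concern holds as a wording conflict with a definite consequence. As stated, the rule in SAP 3.5.1 gives the trial-failure adverse-event endpoint a denominator of 0, where Protocol 10.3 would give up to about 107 at the planned flow. It also narrows the implanter-experience summary relative to Protocol 10.3.

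The impact is limited to descriptive safety endpoints. The primary hypothesis test, the 5% significance level, the sample size and data collection are unaffected. The underlying events remain in the pooled SAP 3.2 summary and the annual reports.

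The figure of 0 rests on the visible definition of the primary analysis population. The figure of 107 rests on full enrollment of 426, on 319 implants, and on all other subjects being trial failures. Because parts of the SAP are redacted, the claim concerns what the visible text prescribes; it does not predict that the final table will be empty.

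**What to change.** In SAP 3.5.1, replace the single population sentence with three statements:

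1. The effectiveness endpoints, and the endpoint on device-, procedure- or stimulation-related events among permanent implants, use the primary analysis population with available data.
2. The trial-failure adverse-event endpoint uses all subjects who received the trial system and failed the trial phase.
3. The summary of procedure-related events by implanter experience uses all subjects with available data, as in Protocol 10.3.

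The no-imputation statement can stay for all of them. Replacing the screen-failure label in SAP 1.3 with a term such as enrolled, system-trial failure would be an optional clarification, not the correction of an error.

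The cost is SAP wording only. Adverse events are already recorded at the trial-implant and end-of-trial visits, so no new data, visits or sample size are needed.

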3.5.2 Additional data

[REDACTED]

4.0 DOCUMENTATION AND OTHER CONSIDERATIONS

4.1 Change in Analysis and Justification

This confidential document is the property of Abbott and shall not be reproduced, distributed, disclosed or used without the express written consent of Abbott.

Statistical Analysis Plan

4.1.1 Imputation

[REDACTED]

4.2 Analysis software

All analyses will be performed using SAS® for Windows, version 9.4 or higher.

5.0 ACRONYMS AND ABBREVIATIONS

Acronym or Abbreviation	Complete Phrase or Definition
ADE	non-serious Adverse Device Effects, which include device, procedure or stimulation related non-serious adverse events
AE	Non-serious Adverse Events not related to device, procedure or stimulation
CEC	Clinical Events Committee
CIP	Clinical Investigation Plan
CRF	Case Report Form
LCB	Lower Confidence Bound
SADE	Serious Adverse Device Effects, which include device, procedure or stimulation related serious adverse events
SAE	Serious Adverse Events not related to device, procedure or stimulation
SAP	Statically Analysis Plan
UCB	Upper Confidence Bound
VAS	Visual Analog Scale (mm)

